Describe the study participants and the population from which they will be drawn. Specify the inclusion and exclusion criteria. If you plan to include children, note their ages and whether you will include children in foster care or who are wards of the State. Note if the participants are particularly vulnerable in terms of cognitive limitations, education, legal migration status, incarceration, poverty, or some combination of factors.

A. Inclusion Criteria:

All participants must be parents/caregivers or index youth enrolled in Project SafeSchools.

Adult participants:

- Have elevated levels of mental distress as reported in a Project SafeSchools assessment.
- Agreement to be re-contacted for future research as part of their Project SafeSchools consent.
- Meeting symptom eligibility criteria as outlined in Table 2 at a screening assessment/baseline visit.

Youth participants:

- Are 11-16 years old
- Agreement from parent/caregiver to be re-contacted for future research from their Project SafeSchools consent form.
- Meeting symptom eligibility criteria based on a self-report screening assessment/baseline visit (outlined in Table 2).

For the inclusion criteria, mental distress is defined as meeting eligibility cutoff scores on the following instruments:

- Adult Participants
 - o General Distress (Kessler)
 - Anxiety (PROMIS)
 - Depression (CESDR-10)
 - o Recent Suicide Ideation (either CESDR-10 or Ideation Questionnaire)
- Youth Participants:
 - Depression (CESDR-10)
 - o Emotional Problems (SDQ Emotional Problems Subscale)
 - Anxiety (SCARED)
 - o Recent Ideation (Ideation question on CESDR-10 or ideation questionnaire)

Table 2. Mental Health Assessments and Eligibility Scores

Mental Health Assessment	Scale	Cut Off Scores for Eligibility
Adult screening tools		
Kessler (Stress)	0-24 scale	13+ is high risk
CESDR-10 (Depression)	0-30 scale	8+ is high risk
CESDR-10 (Recent Suicide Ideation)	0-4	1+ is high risk
PROMIS (Anxiety)	8-40 scale	17+ is high risk
Caregiver report screening tools*		
SDQ (Emotional symptoms)	0-10 scale	5+ is high risk
SCARED (Anxiety)	0 - 82 scale	25+ is high risk
Suicide Ideation	0-4	4 is high risk
Youth self-report		
CESDR-10 (Depression)	0- 30 scale	8+ is high risk
CESDR-10 (Recent Suicide Ideation)	0-4	1+ is high risk
SDQ (Emotional symptoms)	0 – 10 scale	6+ is high risk
SCARED (Anxiety)	0 - 82 scale	25+ is high Risk

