Potential participants will be initially identified by use of existing mental health data collected as part of the Project SafeSchools assessments (IRB No.: 14911). Only caregivers and their youth with elevated mental health scores as indicated by standardized cutoff scores on symptom measures of anxiety, depression, emotional symptoms (youth only), and suicidal ideation (Table 2) and who consented to be contacted about future research as part of their consent provided for Project SafeSchools will be approached for participation in this study. Potentially eligible parent/caregiver participants will be contacted by phone or via an in-person visit to the participant's home by trained study staff to inform them about the study and assess their interest in participating. Study staff will tell potential participant about the study using the recruitment script. If unable to make contact initially, staff will attempt to contact the potential participant until the person can be reached and either agrees to or declines to participate or until staff have attempted to contact the potential participant 8 times, whichever comes first. Parents/caregivers must be contacted first before approaching the youth about participation in the study. If a person declines participation, they will not be contacted again. Potential participant status and attempted contacts will be recorded in REDCap to ensure protocol compliance. Agreement or declining to participate in the research study will never be disclosed.

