Consent, parental permission, and youth assent in this study will be obtained prior to any research-related participation. Study staff who have been trained by JHU will obtain informed consent from participants who do not give online consent. They will be trained in responsible conduct of human subjects research as a part of site training procedures. This will include training in the principle of respect for persons, protecting confidentiality, and the process of informed consent.

b. How, where, and when the consent discussion(s) will occur:

Informed consent and parental permission will be obtained by trained study staff in one of three ways: either online (adult participants only are eligible for this option), orally by phone, or inperson with documentation saved in REDCap. Minor assent will take place by phone or in person. Consent to participate will be obtained prior to the collection of any data. Online or verbal informed consent, permission, and assent will be obtained for all participants.

c. The process for determining whether a potential participant meets eligibility criteria. If you will collect personally identifiable information for screening purposes, collect only data needed for this purpose and explain what will happen to the data for individuals who are not eligible:

During recruitment, study staff will only approach those who were identified as being potentially eligible to participate in this study based on their mental health assessment cut off scores from the Project SafeSchools cohort study. This will be done as part Project SafeSchools existing safety response protocols which includes calling participants with these alerts and facilitating connections to resources in the community. At initial contact with potential participants, study staff will explain the study and ask if they are interested in participating. Potential participants or parents/caregivers of potentially eligible youth will be asked if they need to update their contact information (stored as part of Project SafeSchools) and provide separate contact information for their child if needed. This information is needed for screening purposes (if screening is done at a separate visit), but also to ensure delivery of intervention materials and possibly study assessments if they enroll. If they are ineligible or decide not to enroll, their contact information under this CiM/HSP protocol will be destroyed.

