If a potential participant is interested, depending on preference, consent/assent will be administered during the same visit or scheduled for another day. If the person is not interested, they will be thanked for their time and continue to receive support for their mental health concerns and safety and continue to be enrolled in the Project SafeSchools cohort study. Study staff will document their decision in REDCap, and they will not be approached again about participation in +CiM/HSP.

As part of the consent process, individuals will consent to accessing their data collected in the Project SafeSchools cohort study. Eligibility screening for the +CiM/HSP study will occur after consent to participate and as part of the baseline assessment (Figure 1). An individual must score at or above the cut-off score on any of the mental health screening tools (see Table 2) to be included. If the person is determined to be ineligible after this screening, they will be notified by the study staff and informed that this ineligibility for +CiM/HSP study will in no way affect their participation in the Project SafeSchools study. If the participant is eligible for +CiM/HSP, they will continue with the rest of the assessment and other study activities.

This study is an individual intervention, not based on dyads. Only those caregivers and youth with elevated mental health scores at screening will participate. A parent/caregiver and youth can participate without the other being enrolled.

d. Whether you will obtain a signature from the participant or will use an oral consent process:

We will use an online or oral consent/permission/assent process due to COVID and to protect privacy.

e. Whether you will obtain a legally authorized representative's signature for adults lacking capacity:

N/A

f. If children are included in the study, if and how you will obtain assent from them:

Assent will be obtained following parent permission to be involved in the study.

g. If children are included in the study, how you will obtain permission for them to participate from their parent, legal guardian, or other legal authority (if child is in foster care or under government supervision). If any of the children are "wards of the state", additional regulatory requirements will apply:

Parent permission will be obtained orally either over the phone or in-person prior to youth assent.

h. If you are seeking a waiver of informed consent or assent, the justification for this request:

N/A

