Analysis for all aims: Are planned statistical analysis will focus on the parent/caregiver surveys, given anticipation that sample sizes will be higher for this group. However, we will analyze the youth self-report descriptively. For adult outcomes, we will examine change over time on outcome measures and differences on these trajectories by study arm (Aim 1) or by timepoint (Aim 2). Additional analyses may also occur depending on guidance from our Community Advisory Boards. Every effort will be made to generate complete data; however, inevitably some data will be missing, and the methods recommended by Schafer and Graham (2002) will be used to evaluate missing data assumptions and guide the analyses. Based on the amount of missing data and evidence for a Missing At Random versus Missing Not At Random missing data mechanism, missingness will be addressed. The missing data approach will be finalized before the outcome analysis. Our analytic plan will also leverage data collected as part of their participation in the Project SafeSchools cohort study (see section XI for details). This will serve as a historical control comparison period for Aim 2, as well as provide a better understanding of longer-term impact of the interventions.

5. Answer the following **if they are relevant to your study design**:

A. If the study has different arms, explain the process for assigning participants (intervention/control, case/control), including the sequence and timing of the assignment.

Participants will be block randomized with blocking on age (e.g., caregiver vs. youth) and gender. A randomization table will be created in a statistical software (e.g., Stata, SAS, R) and incorporated into REDCap. Randomization and assignment of intervention or control groups will occur following consent by a study team member. The study team member will only need to select the randomization option within the participant's study REDCap form for randomization to occur.

B. If human biospecimens (blood, urine, saliva, etc.) will be collected, provide details about who will collect the specimen, the volume (ml) and frequency of collection, how the specimen will be used, stored, identified, and disposed of when the study is over. If specimens will be collected

for use in future research (beyond this study), complete the "Biospecimen Repository" section below.

N/A

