Data from Project SafeSchools (IRB No.: 14911) will be used to help in estimating the stability of psychosocial functioning prior to interventions as well as serve as a longer-term follow-up of the impact of interventions over time. For our primary Aim, estimating the effectiveness of +CiM/HSP, we will used mixed-effects models to compare symptom scores across arms with our main outcome time point to be analyzed based on the Wave 3 outcome time point in Project SafeSchools, estimated to be approximately 3-6 months after enrollment into +CiM/HSP. For Aim 2, we will use a within subjects design to measure differences in symptoms prior to starting the +CiM/HSP intervention components compared to after completion of the intervention components using the Project Safe Schools Wave 1, 2, and 3 data collection timepoints. This analysis will focus on the measures that are common to both the +CiM/HSP protocol and the Project SafeSchools data (e.g.,

IRB #00020570 +CiM/HSP research plan v7 14Nov2022

PIs: [name] (Faculty PI) & [name] (Navajo Community PI)

Adult self-report on depression and anxiety symptoms and caregiver report on strengths and difficulties, resilience items).

B. Participants:

1. Describe the subjects who provided the original data and the population from which they were drawn.

Study subjects are all youth ages 11-16 or adult caregivers over the age of 18 that either attend or have a student attending a school serving enrolled tribal members of the White Mountain Apache Tribe or the Navajo Nation.

Note: If you are receiving, accessing, or using data from a U.S. health care provider, the need for HIPAA review is likely. If you plan to bring identifiable health information from a foreign country to a U.S. covered entity (e.g., lab at the Hopkins SOM), HIPAA may be triggered. If either of these conditions is met, check "yes" to the HIPAA question in the PHIRST application.

2. If you plan to analyze human specimens or genetic/genomic data, provide details about the source of those specimens and whether they were collected using an informed consent document. If yes, explain whether your proposed use is "consistent with" the scope of the original consent, if it potentially introduces new analyses beyond the scope of the original consent, and/or if it introduces new sensitive topics (HIV/STDs, mental health, addiction) or cultural/community issues that may be controversial.

N/A

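### Aim 2 takes a within-person fall as evidence on the coping plan, but adults are selected on high scores, both arms get the plan, and the reference wave is not fixed

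*Combined protocol and SAP*

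**What the plan says.** Section I lists Aim 2 among the primary aims. It is to evaluate any benefit of coping plans and check-ins within subjects, and Hypothesis 2 predicts lower symptoms than at previous assessments. The overview in Section I gives the coping plan to both arms.

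Section V.C.4 (data analysis plan) says of the parent-cohort data: "This will serve as a historical control comparison period for Aim 2". Section XI.A.3 adds: "For Aim 2, we will use a within subjects design to measure differences in symptoms prior to starting the +CiM/HSP intervention components", compared with symptoms after completion, "using the Project Safe Schools Wave 1, 2, and 3 data collection timepoints". The same section says that cohort data "will be used to help in estimating the stability of psychosocial functioning prior to interventions". It places Wave 3 about 3 to 6 months after enrolment, as the main outcome point for Aim 1.

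Selection happens twice. Adults must "Have elevated levels of mental distress as reported in a Project SafeSchools assessment" (Section IV.A), and Section V.A.1 restricts the approach in the same way: "Only caregivers and their youth with elevated mental health scores as indicated by standardized cutoff scores on symptom measures". They are then re-screened at the pilot baseline: "An individual must score at or above the cut-off score on any of the mental health screening tools" (Section V.B.1.c).

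**The concern.** People chosen because a fluctuating score was high tend to score lower next time, treated or not. Hypothesis 2 predicts a change in that same direction. Because every participant gets the coping plan, no randomised group shows what would have happened without it.

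Several other influences cannot be separated from the coping plan:

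- time trend between waves;
- contact under the cohort's "existing safety response protocols which includes calling participants with these alerts and facilitating connections to resources in the community" (Section V.B.1.c);
- outside care that does not arise from the programme's own referrals (Section V.C.5.F.f);
- the caring messages, which half the participants also receive. The plan does not say whether Aim 2 pools the arms.

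At stake is a fall being reported as coping-plan benefit when the true effect is zero. Section III.A says promising results will inform a fully powered study.

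**Working it through.** **The plan's own figures.** Section III.B gives 118 × 0.8 = 94 enrolled and 94 × 0.8 = 75 analysed adults. A two-sample t calculation with 37.5 per arm, two-sided 0.05 and 80% power gives d = 0.656, which agrees with the stated 0.66. Table 1 follows: 0.66 × 6.4 = 4.2 and 0.66 × 5.3 = 3.5. These figures concern Aim 1. No power or expected change is stated for Aim 2.

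**Inputs for the illustration.**

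- From Section III.B: n = 75; CESDR-10 SD 6.4 (described only as baseline, taken here as the whole-cohort SD); 44% eligible (the plan's figure for any criterion, applied here to CESDR-10 alone).
- From Table 2: cutoff 8.
- Assumed, not in the documents: zero true effect; normal scores; wave-to-wave correlation r = 0.5, 0.8, 0.9, either equal between all time points (exchangeable) or decaying with distance (first-order autoregressive); a paired t-test against Wave 3.
- Time order: Wave 1, Wave 2, pilot baseline, Wave 3.

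**Hand check, one selection step.** With 44% at or above 8, z = 0.151 and the mean is 8 − 6.4 × 0.151 = 7.03. The expected fall from the selecting score is SD × (1 − r) × φ(z)/0.44. Here φ(0.151) = 0.3944 and 0.3944/0.44 = 0.896. So 6.4 × 0.896 × (1 − r) = 2.87, 1.15 and 0.57 points at r = 0.5, 0.8 and 0.9.

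**Two selection steps.** Requiring a score of 8 or more at the alert wave and again at the pilot baseline was simulated (2 million draws per cell). With the alert wave as reference and exchangeable correlation, the falls are 2.14, 0.71 and 0.33 points, and the SDs of the differences are 5.84, 3.87 and 2.78. The noncentrality is fall/SD × √75, that is 3.17, 1.59 and 1.03. A t-test on 74 df then declares benefit in 88%, 35% and 17% of trials, against a nominal 2.5%.

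Other combinations, same assumptions (repeat runs agree within about 2 percentage points):

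| Alert wave | Reference | Correlation | Spurious fall, r = 0.5 / 0.8 / 0.9 | False benefit |
|---|---|---|---|---|
| Wave 1 | Pilot baseline | Exchangeable | 2.1 / 0.7 / 0.3 | 88% / 35% / 17% |
| Either | Wave 1 or Wave 2 | Exchangeable | 0.7 / 0.2 / 0.1 | about 16% / 7% / 5% |
| Either | Wave 1 | Autoregressive | 0.4 / 0.1 / 0.0 | about 6% / 3% / 3% |
| Either | Wave 2 | Autoregressive | 1.9 / 0.9 / 0.45 | about 62% / 32% / 17% |
| Wave 2 | Wave 1 | Both | near 0 | 2–3% |
| Wave 1 | Wave 2 | Exchangeable | near 0 | 2–3% |
| Wave 1 | Wave 2 | Autoregressive | about 1.8 to 0.6 | about 55% / 46% / 28% |

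**A more realistic selection rule.** Two or three qualifying instruments, skewed 0–30 scores and re-screen loss were applied together, with the alert wave as reference. False benefit is then 31–41%, 12–14% and 7–9% (exchangeable, n = 46–62), or 35–64%, 16–27% and 10–15% (autoregressive, n = 39–62).

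**Would a stability contrast correct it?** Take the Wave 2–3 change minus the Wave 1–2 change, where negative favours benefit. At r = 0.5, 0.8 and 0.9, with zero effect, it gives:

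- Wave 1 alerts: +2.1, +0.7, +0.3 (exchangeable); −0.6, −1.0, −0.6 (autoregressive).
- Wave 2 alerts: −4.3, −1.4, −0.7 (exchangeable); −6.4, −2.6, −1.3 (autoregressive).

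The sign depends on facts that the plan does not fix.

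**The case against.** A reader might infer that the plan credits the coping plan with any fall. The documents do not say so: Hypothesis 2 predicts a reduction and gives no attribution rule. A reader might also infer that no earlier wave is identified. That is too strong, because Section XI.A.3 lists three waves and places Wave 3 after enrolment, so Waves 1 and 2 are the implied earlier period. What is missing is which of them, or the pilot baseline, is the reference and how they are combined.

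Outside care is not wholly a confounder. Section I describes the programme as including facilitated connections to care, and under Section V.C.1 the check-ins make referrals. Care reached that way is part of what is being evaluated. Cohort alert calls may also have operated before enrolment.

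The paired test is a stand-in. Section V.C.4 speaks of change over time by time point, and a model averaging Waves 1 and 2 does better: under an either-wave alert, about 20%, 8% and 6% false benefit (exchangeable) or 30%, 12% and 7% (autoregressive). That reduces the artefact without removing it, and the plan specifies no such model.

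Finally, the study is a pilot, the template asks for a brief plan, Section XI.A.3 uses the phrase primary aim for Aim 1, and youth self-report is descriptive only. These points limit the severity. They do not make the within-person comparison a test of coping-plan benefit.

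**Conclusion.** The concern holds in conditional form. Following Aim 2 as written can show a fall in the hypothesised direction when the coping plan has no effect, and neither the historical-control statement nor the stability statement specifies a correction. The size depends strongly on the alert wave, the reference wave and correlations that the documents do not give. It runs from near zero to 2.1 points in the exchangeable single-scale cases shown.

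The 88% figure should not be read as the expected error rate. It needs a single alert wave used as reference, one scale, r = 0.5 and n = 75 together. Nor is it a ceiling for every correlation pattern, since autoregressive correlation can give more.

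A better reference wave would address regression to the mean only. Time trend, cohort alert contact and non-programme care would still be mixed with the coping plan. It would be wrong to infer that the trial's randomised result is compromised: Aim 1 compares arms selected in the same way and is unaffected. This should be fixed before analysis.

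**What to change.** In Section I (Aim 2 and Hypothesis 2), Section V.C.4 and Section XI.A.3:

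- Restate Aim 2 as an estimate of within-person change, giving means with 95% confidence intervals at Waves 1 and 2, pilot baseline and Wave 3. It should not be a test of coping-plan benefit.
- Name the reference wave in advance.
- Derive the wave that raised each participant's alert, and report change by alert wave.
- Report by arm, or state that the arms are pooled.
- State that the pilot baseline is itself a selecting score.
- State that regression to the mean, time trend, cohort alert contact and care outside the programme's referrals cannot be separated from the coping plan, so a fall alone will not be reported as coping-plan benefit.

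The cost is wording and one derived variable from cohort data already used to identify participants. No new visits, data collection or participants are needed. The downside is that Aim 2 no longer supports a causal benefit claim.
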